8.1.6 Performing diagnostic effectiveness analysis

## **8.2 Part II Assessment of the association between lower genital tract pathogen infection, CST and infertility using newly developed assays**

8.2.1 Select infertile women of childbearing age who meet the criteria for nadir to sign informed consent and be enrolled in the study.

8.2.2 Completion of an information collection form to obtain information on **confounding factors that** may affect this study (age, weight, height, ethnicity, ancestry, place of long residence, number of pregnancies and births, time of last menstruation and menstrual cycle, duration of infertility, relevant diagnoses leading to infertility, etc.), which is collected daily by the information management specialist and kept.

8.2.3 Sample collection: take cervical canal and vaginal secretions during routine gynecological examination and routine leucorrhea examination secretions during routine consultation. ④ Place the swab head in sterile storage solution and tighten the cap ⑤ Label the bottle with patient information ⑥ Store in 4°C refrigerator.

8.2.4 Isolation and extraction of pathogen DNA.

8.2.5 Detection of microorganisms in the lower genital tract by a constructed MALDI-TOF MS assay.

8.2.5 Uniform disposal of remaining specimens in accordance with medical waste after sample testing is completed.

8.2.6 Statistical analysis to assess the correlation between various pathogenic infections and CST status and infertility separately

[figure not shown]
8.2.7 Statistical analysis to assess differences in CST status between infected and uninfected individuals with various pathogens

## **8.3 Sample preservation and handling**

[figure not shown]
All specimens will be stored in a 4°C refrigerator on the same day and DNA will be extracted within 24 hours. DNA specimens will be marked with specimen number and sampling time as required and then stored in a -80°C refrigerator in the gynecology department of the central laboratory, and the remainder will be disposed of in accordance with the medical waste disposal process. After the DNA specimens are tested and the results are analyzed, they will be disposed of according to the medical waste disposal process.

## 9. Research Flow Chart

Part I.

Part II.

## 10. Ending evaluation indicators

10.1 Mycoplasma solium, Mycoplasma humanum, Chlamydia antigen, and gonococcus were recorded as positive or negative according to the clinical report.

10.2 MALDI-TOF MS test results were recorded as: microbial type, positive, negative

## 11. Security evaluation

This study involves only 1 vaginal and cervical secretion collection, which is consistent with HPV sampling during cervical screening in routine clinical testing and does not cause additional collection points or additional consultation costs, and is safe. It may cause pain and a little bleeding to the patient, neither of which will have any impact on the patient's health. Inform the patient before the operation to avoid causing panic. If the patient has intercourse immediately after the test or performs inappropriate transvaginal operations that may lead to infection, the patient is advised to avoid intercourse, sitz baths and other transvaginal operations without professional medical guidance for 3 days after sampling.

### 11.1 Vital signs observation and laboratory tests

Pain: WHO Pain Classification

Bleeding: ①Bleeding volume assessment: (according to the bleeding area assessment method in the Guidelines for the Diagnosis and Treatment of Abnormal Uterine Bleeding); ②Blood count

Infections: white belt routine, blood count

### 11.2 Adverse Events

(List of possible adverse events, all possible adverse reactions in the study should be fully considered, and should include possible adverse reactions in all aspects of laboratory tests (e.g. blood collection, ECG, imaging, etc.), interventions (e.g. drug treatment, surgical treatment, etc.) and other non-interventions (e.g. postural tests, scale tests, questionnaires, etc.), and evaluate the severity of the adverse reactions . (The same should also be reflected in the informed consent form, fully informed to the subject.)

Pain: pain can be graded (0-4),  $\geq 1$  noted as an adverse event

Grading: Grade 0: No pain.

Grade 1 (mild pain): painful but not severe, tolerable, sleep is not affected

Grade 2 (moderate pain): pain is obvious and unbearable, sleep is disturbed,

analgesics are requested

Grade 3 (severe pain): severe pain, unbearable sleep severely disturbed, analgesics needed

Bleeding: small amount 0.1-1ml, medium amount 1-5ml, large amount >5ml, medium and large amount of bleeding recorded as adverse events

Infections.

Mild infection - increased cervical or vaginal discharge, white belt routine indicating cleanliness grade III or leukocytes +++

Moderate - Large amount of discharge with abnormal characteristics, white belt routine indicating cleanliness IV or white blood cells ++++ or BV positive

Severe - with pain or pressure and the presence of infection are recorded as adverse events

### 11.3 Pre-assessment of relevant risks and disposal plans

Pain:  $\geq$  grade 1 may be given pain medication

Bleeding: Vaginal gauze is used to stop heavy bleeding

Infection: mild infection - vaginal douching; moderate - vaginal medication based on routine leucorrhoea test results; severe - vaginal medication combined with oral anti-infection therapy based on routine leucorrhoea test results

\*The study sponsor will bear all the costs related to the above adverse events and exempt the subjects from the costs related to the adverse events, including all the costs related to the adverse events during and after the end of the trial.

## 12. Data management and statistical analysis

(The following points should be clarified.

a. Whether data collection, processing and analysis are managed by a dedicated person and the manager has a GCP certificate.

b. the use of questionnaires, completed by patients with the assistance of the investigator, to complete the questionnaires and collect data.

c. **Using Empower statistical software**, sensitivity (Se), specificity (Sp), positive predictive value (PV+), and negative predictive value (PV-) were used for the first part **of the diagnostic efficacy assessment**, and chi-square test, rank sum test, stratified analysis,

and logistic regression correlation analysis were used for the second part.

d. Establish standard operating procedures and quality control procedures for each part of the operational process, and the experimental test report form must be complete with all items and all reports written using uniform standards to ensure **accurate and valid data**.

e. All data are collected and managed in a confidential account, and the paper files are stored in the department's clinical research file safe, so that any non-data administrator conducting data analysis cannot obtain patients' personal privacy information such as name, ID number, telephone number, and address.

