	
8) Have the habit of smoking and drinking
 
Control group:
 
 
1) Pregnancy by various assisted reproductive means
 
2) Patients with malignant tumors
 
3) Patients with autoimmune diseases
 
4) Patients with severe heart, kidney and other basic diseases
 
5) Patients who consumed antibiotics 3 days before the examination
 
6) Have the habit of smoking and drinking
 

Exclusion Criteria
	
All samples tested in Part I were acquired standards with no inclusion criteria; Part II:
 
Case group:
 
 
1) Infertility due to malformation of reproductive tract
 
2) Infertility caused by endocrine factors such as polycystic ovary syndrome, premature ovarian failure and severe hyperthyroidism
 
3) Infertility due to male factors
 
4) Patients with malignant tumors
 
5) Patients with autoimmune diseases
 
6) Patients with severe heart, kidney and other basic diseases
 
7) Patients who consumed antibiotics 3 days before the examination
 
8) Have the habit of smoking and drinking
 
 
Control group:
 
 
1) Pregnancy by various assisted reproductive means
 
2) Patients with malignant tumors
 
3) Patients with autoimmune diseases
 
4) Patients with severe heart, kidney and other basic diseases
 
5) Patients who consumed antibiotics 3 days before the examination
 
6) Have the habit of smoking and drinking
 

Ending evaluation
	
Main indicators: microbiological test results, are recorded as negative, positive

indicators	
Safety evaluation indicators	Pain indicators: pain score; bleeding indicators: bleeding volume assessment (blood staining area method), blood routine; cervical and vaginal infection: white belt routine

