## **1. 2 Current status of domestic and international research.**

Sexually transmitted infections (STIs) are a major global health problem, with

127 million and 27 million adults worldwide having *Chlamydia trachomatis* and gonococcal infections in 2012, according to statistics. . Both infections are mainly asymptomatic and curable, but if untreated or ineffective, they can lead to pelvic inflammatory disease, infertility and ectopic pregnancy, and *Chlamydia trachomatis* infection is also associated with a variety of adverse pregnancy outcomes, such as chorioamnionitis, preterm delivery and low birth weight . Reproductive mycoplasma infections are as high as 2.0%-7.3% and are thought to be associated with UTIs, cervicitis, pelvic inflammatory disease, and infertility .

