## **6. estimation of sample size and grouping method**

### 6.1 Estimation of sample size

#### 6.1.1 Part I: Comparison of sensitivity of dose information between the two groups

Single and mixed standard bacterial solutions and blank controls were 11 in total, so the chance of the appearance of four microorganisms in various standard strain solutions was 0.18, and different studies showed that the culture sensitivity of gonococci, lactobacilli, mycoplasma, and chlamydia was 40-60% and specificity 95-98%; time-of-flight mass spectrometry detection was >99% in different studies, and the parameters were brought into

PASS according to  $\alpha=0.1$  Software calculation path: Tests for Two Independent Sensitivities,  $N=44-72$ , taking the least integer multiple of 11 for  $>72$ , i.e., 77 cases in each group

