#### 6.1.2 Part 2: Comparison of independent sample rates between the two groups

Comparison of the independent sample rates of the two groups: the infection rate of at least one pathogen in the whole population is about 0.01%, and the infection rate of patients who visited our hospital for infertility is about 0.46%, and this data was brought into SPSS software: Confidence Intervals for the Difference Between Two Proportions,  $n=114$  cases, so 114 cases were included in the experimental group and the control group each

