### 8. Research steps

#### **8.1 Part I. Development of a rapid detection method based on MALDI-TOF MS for simultaneous detection of multiple pathogens and CST in the lower genital tract and evaluation of diagnostic efficacy**

8.1.1 Find the relatively conserved regions of virulence factor sequences of each pathogen according to the database, intercept the specific sequences from the conserved regions of each pathogen to design multiplex PCR amplification primers and single base extension (SBE) primers for each strain to construct MALDI-TOF MS assays.

8.1.2 Purchase standard pathogen strains, culture standard concentrations (i.e., high concentrations) of standard pathogens using the culture method to identify standard pathogens and their activities

8.1.3 Formulation of single, mixed and negative control standards with standard pathogens.

8.1.4 Gold standard: The actual pathogen type added to the standard is the gold standard.

8.1.5 Detection of standards at gradient dilution concentrations by incubation method and MALDI-TOF MS, respectively.

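### Part I predictive values come from laboratory-made standards, so they describe the panel as mixed and cannot be read as predictive values in patients

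*Combined protocol and SAP*

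**What the plan says.** Section 12, item c, names four measures for the Part I assessment of diagnostic efficacy: Se, Sp, PV+ and PV-. On the last two it says "positive predictive value (PV+), and negative predictive value (PV-) were used for the first part". It neither limits them to the test panel nor plans to recompute them at a clinical prevalence.

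The Part I samples are not patients:

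- Section 1 (exclusion criteria): "All samples tested in Part I were acquired standards with no inclusion criteria".
- Section 8.1.3: the team makes up single, mixed and negative standards.
- Section 8.1.4, on the reference: "The actual pathogen type added to the standard is the gold standard".
- Section 8.1.5: "Detection of standards at gradient dilution concentrations by incubation method and MALDI-TOF MS, respectively".

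Section 6.1.1 counts 11 solutions in total, "so the chance of the appearance of four microorganisms in various standard strain solutions was 0.18". It does not list the 11 solutions or say that 0.18 is per organism. For the new assay it says only that "time-of-flight mass spectrometry detection was >99% in different studies", without naming the measure.

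**The concern.** A predictive value is the probability that a tested subject is truly positive or negative, given the result. It needs a share of positives that means something in the population of interest. Here that share follows from how the tubes are filled, so the same assay with the same accuracy would give different PV+ and PV- under another mix.

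Two of the four named efficacy measures are affected. Reported without a label under diagnostic efficacy, they invite comparison with clinical predictive values. The size of any PV- gain of MALDI-TOF over culture would also look like a property of the two methods, although it depends in part on the mix.

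**Working it through.** **Inputs**

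- Share of positives: 0.18 (section 6.1.1). 2/11 = 0.1818 fits this as a share per organism, which is an inference.
- Culture: Se 40-60%, Sp 95-98% (section 6.1.1). I take 0.50 and 0.95 from within these ranges.
- MALDI-TOF: above 99%, measure not named. I assume Se = Sp = 0.99, then 0.999.
- Prevalence for comparison: section 1.2 says "Reproductive mycoplasma infections are as high as 2.0%-7.3" (per cent). Section 6.1.2 says "the infection rate of patients who visited our hospital for infertility is about 0.46", printed with a percent sign. It may be meant as a proportion, so I show both readings.

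**1. The plan's own figure.** Section 6.1.1 gives N = 44-72, raised to 77 per group. Power and sidedness are not stated. I assume one-sided alpha 0.1, 80% power, a continuity-corrected comparison of two proportions and MALDI-TOF Se 0.999. Culture Se 0.40 then needs 8 positives per group, and 8/(2/11) = 44. Culture Se 0.60 needs 13, and 13/(2/11) = 71.5, so 72. The next multiple of 11 is 77. The match supports reading 0.18 as 2 of 11 per organism. It also shows that the sample size rests on sensitivity, not on predictive values.

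**2. Formulas**, with p the share of positives:

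PV+ = Se·p / [Se·p + (1-Sp)(1-p)]

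PV- = Sp(1-p) / [Sp(1-p) + (1-Se)p]

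**3. Same test, different mix.** Culture at 0.50/0.95, with an organism in 1, 2 or 3 of the 11 solutions:

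- 1 of 11: PV- = 0.95×10 / (0.95×10 + 0.5×1) = 9.5/10 = 95.0%
- 2 of 11: 8.55/9.55 = 89.5%
- 3 of 11: 7.6/9.1 = 83.5%

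The conclusion does not need the 2-of-11 reading. Four single solutions, six pairs and one blank also total 11 and put each organism in 4 of 11. MALDI-TOF PV+ at 0.99/0.99 is then 3.96/4.03 = 98.3%, against 1.98/2.07 = 95.7% at 2 of 11.

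**4. Panel against other prevalences.** PV- gain is MALDI-TOF 0.99/0.99 minus culture 0.50/0.95.

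| p | PV+ at 0.99/0.99 | PV+ at 0.999/0.999 | PV- gain, points |
|---|---|---|---|
| 0.18 (panel) | 95.6% | 99.5% | 10.1 |
| 7.3% | 88.6% | 98.7% | 3.9 |
| 2.0% | 66.9% | 95.3% | 1.0 |
| 0.46% (as printed) | 31.4% | 82.2% | 0.2 |
| 0.46 (as a proportion) | 98.8% | 99.9% | 30.1 |

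For example, PV+ at 2.0% is 0.0198/(0.0198 + 0.0098) = 66.9%. The PV- gain at 0.18 is 0.8118/0.8136 - 0.779/0.869 = 99.8% - 89.6% = 10.1 points before rounding.

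For given Se and Sp, the panel overstates PV+ and understates PV- where prevalence is below 0.18, and does the reverse above it.

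**5. Pooled Se also moves with the panel.** Because graded dilutions are tested, pooled Se depends on how many positives sit at each level. With assumed Se of 0.90 at high and 0.10 at low concentration, pooled Se is 0.70, 0.50 or 0.30 if 75%, 50% or 25% of positives are at the high level (for example 0.75×0.90 + 0.25×0.10 = 0.70). Replacing PV+ and PV- with a single pooled Se would leave part of the problem in place.

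**The case against.** The strongest reply is that the plan hides nothing and claims little. It says openly that Part I uses standards, keeps Se and Sp beside the predictive values, and never says that PV+ or PV- applies to patients. No sample size and no Part II analysis uses them. All of this stands, and it limits the consequence to how Part I efficacy is reported.

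A reader might infer two stronger things that the documents do not support:

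- **That the mix alone fixes PV+ and PV-, so any PV- advantage over culture is an artefact.** PV+ and PV- depend jointly on Se, Sp and the mix. A test better on both Se and Sp has higher PV+ and PV- at every prevalence, and the four PV- gains above at other prevalences are all positive, as is the panel's. The mix changes the size of the gain, not its existence.
- **That the panel flatters the assay by a known amount.** At 0.999/0.999 the fall in PV+ from 0.18 to 2.0% is about 4 points, not 29, and above 0.18 the direction reverses. The 2.0% is a mycoplasma rate and may not fit the other organisms, lactobacilli in particular. The rate in section 6.1.2 appears to be for any pathogen, and its unit needs reconciling.

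It can also be said that a label would be enough and that removal is not required. That is fair, and the fix allows either.

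**Conclusion.** The point holds as one about analysis and interpretation. Followed exactly, item c yields predictive values that vary with a mix the study team chooses. They describe the panel and should not be presented as predictive values in patients.

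That conclusion rests only on what the plan says about its standards and on the formulas. Its size does not: it depends on the true Sp, which the plan does not state for MALDI-TOF, and on prevalence per organism. The 2-of-11 layout is inferred and is used only for illustration. The change is worth making before Part I is reported, but it does not undermine the design, the 77 per group or Part II.

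**What to change.** In section 12, item c:

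1. Make Se and Sp per organism the Part I efficacy measures, with 95% confidence intervals. The figure of 77 suggests seven repeats of 11 solutions. If so, the intervals must allow for repeated testing of the same standards. Exact binomial intervals are suitable only if the samples are independent.
2. Show Se by dilution level, and state how many standards of each organism are tested at each level.
3. Drop panel PV+ and PV-, or keep them only with a label saying they are specific to this panel.
4. Give any predictive values meant for patients only as Bayes projections over a stated prevalence range per organism, with uncertainty in both Se and Sp carried through. Label them illustrative, since accuracy on made-up standards may not carry over to patient samples. Use the infertility-clinic rate only once section 6.1.2 is reconciled.

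**Cost.** The predictive-value change is wording, plus one table if projections are shown, with no new data. Stating counts per dilution level means settling details that sections 8.1.3 and 8.1.5 leave open. Precision will be low. If each organism is in 2 of 11 solutions, 77 samples hold 14 positives. Two dilution levels would leave 7 each, and even 7 of 7 detected has an exact 95% lower limit of 0.025^(1/7) = 0.59, if independent. Projections will have wide intervals and may look less favourable than the panel values.

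### For the pathogen–infertility comparisons, standard logistic regression often has no finite odds ratio at 114 per group, and section 12 names no sparse-data method

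*Combined protocol and SAP*

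**What the plan says.** Section 12, item c, gives the whole Part II analysis as a list of methods. It opens with "chi-square test, rank sum test, stratified analysis", and the regression is covered by one further phrase: "and logistic regression correlation analysis were used for the second part". It does not state the model, the covariates, the estimator or what happens when a cell is empty. No exact or penalised method is named.

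Section 6.1.2 supplies the only rates tied to the Part II sample size. On the control side it says "the infection rate of at least one pathogen in the whole population is about 0.01", a figure printed with a percent sign. On the case side, again with a percent sign after the figure, it says "the infection rate of patients who visited our hospital for infertility is about 0.46". They lead to the group size: "so 114 cases were included in the experimental group and the control group each".

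Section 8.2 sets the scope. Step 8.2.6 reads "Statistical analysis to assess the correlation between various pathogenic infections and CST status and infertility separately", so pathogens and CST are separate exposures. Step 8.2.7 adds a comparison within the sample: "Statistical analysis to assess differences in CST status between infected and uninfected individuals with various pathogens". No CST rate appears anywhere.

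Section 1.2 of the background gives 2.0% to 7.3% for reproductive mycoplasma infection alone.

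**The concern.** In this case-control comparison the odds ratio for infection is finite under maximum likelihood only if each group has at least one infected and at least one uninfected woman. If all infected women are in one group, the estimated coefficient runs off to infinity, and its Wald interval is uninformative. Adding covariates does not help, because the infection term still separates the groups. If nobody is infected, the term cannot be estimated at all.

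The planning rates are low and the groups small, so an empty infected-control cell is a likely outcome and the plan should provide for it. Without a stated rule, the analyst must choose a method after seeing the empty cell, or report an estimate that software prints but that has no meaning. The second half of study aim 2, the link between pathogen infection and infertility, would then have no defensible effect size.

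**Working it through.** **Inputs.** n = 114 per group (section 6.1.2). Infection rates p₀ (controls) and p₁ (cases) under three readings:
- A: 0.01% and 0.46%, as printed in section 6.1.2.
- B: 1% and 46%, assuming the percent signs are slips for the proportions 0.01 and 0.46.
- C: 2.0% and 7.3%, an illustrative use of the mycoplasma range in section 1.2. The document does not assign these values to cases and controls.

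**The plan's own figure.** 114 cannot be confirmed. The procedure named is "Confidence Intervals for the Difference Between Two Proportions", but neither the interval width nor the confidence level is given for Part II. With assumed widths, 114 can be nearly matched under A or B:
- B: a 95% continuity-corrected Newcombe–Wilson interval of total width 0.20 needs 115 (width 0.2001 at 114).
- A: a 95% Wald interval of total width 0.025 needs 116.

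So 114 does not settle which rates were meant.

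**Formulas.**
- P(no infected control) = (1 − p₀)^114; P(no infected case) = (1 − p₁)^114.
- P(no infected woman) = the product of these two.
- P(finite unadjusted OR) = [1 − (1 − p₀)^114] × [1 − (1 − p₁)^114]. The chance that a whole group is infected is negligible.
- Expected count in each infected cell, groups pooled = 114 × (p₀ + p₁)/2.

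**Reading A.**
- 0.9999^114 = 0.9887; 0.9954^114 = 0.5912.
- P(no infected woman) = 0.9887 × 0.5912 = 0.584.
- P(finite OR) = 0.0113 × 0.4088 = 0.0046.
- Expected infected women: 114 × 0.0001 = 0.011 controls and 114 × 0.0046 = 0.52 cases. Expected infected cell: 0.27.

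**All readings.**

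| Reading (controls, cases) | P(no infected control) | P(finite OR) | Expected infected cell |
|---|---|---|---|
| A: 0.01%, 0.46% | 98.9% | 0.46% | 0.27 |
| B: 1%, 46% | 31.8% | 68.2% | 26.8 |
| C: 2.0%, 7.3% | 10.0% | 90.0% | 5.3 |

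If there were no difference and both groups had 2.0%, P(finite OR) would be (1 − 0.0999)² = 81%.

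**Single pathogens.** No single pathogen can be more common than any pathogen. As an assumption, split reading B evenly over four organisms, giving 0.25% and 11.5%. Then P(no infected control) = 0.9975^114 = 75%, and the odds ratio for a given pathogen is finite in 25% of studies.

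**What a better estimator can and cannot do.** A penalised or exact method gives a usable estimate or bound when one group has no infected woman. It cannot help when nobody is infected, which is 58% of studies under A. Under A, Fisher's test reaches p < 0.05 with probability of about 0.002%. A finite maximum-likelihood odds ratio in 80% of studies would need about 16,100 women per group.

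**The case against.** The strongest objection is that the fault lies in section 6.1.2, not section 12. An any-pathogen rate of 0.01% cannot stand beside 2.0% to 7.3% for mycoplasma alone, so reading A is doubtful, and the 0.46% result depends on it. If A is true, no change of method saves 114 per group. This stands, and it is why the rates must be reconciled first. It does not dispose of the point: under B, 32% of studies still have no infected control, and under C about 10% have no finite odds ratio.

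A second objection is that the plan says only logistic regression, so a penalised fit is not ruled out. That is fair. The result is therefore stated for standard maximum likelihood, the usual meaning when no estimator is named. Leaving the choice open until an empty cell is seen is itself a weakness.

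A reader might infer two stronger claims that the documents do not support:
- **All of Part II is unusable.** The rates concern pathogen infection only. With no CST rate stated, nothing shows that CST against infertility fails. At an assumed 10% and 20%, the expected cell is 17.1 and the odds ratio is finite in over 99.99% of studies. Step 8.2.7 is exposed only because it needs enough infected women.
- **Chi-square is invalid throughout and overstates the evidence.** Under B its expected cell is 26.8, so the any-pathogen test is sound. With 4 against 0 infected, the uncorrected test gives p = 0.044 and Fisher 0.12, which looks alarming. But section 12 does not say uncorrected, and the Yates correction gives 0.13. Enumerating the uncorrected test at a nominal 5%, with equal rates in both groups, gives a true type I error of 0.2% at 0.46%, 1.8% at 1%, 4.3% at 2% and 4.6% at 5%. At 7.3% it is 5.3%, close to nominal.

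**Conclusion.** The point holds for the pathogen–infertility odds ratios. Under standard maximum likelihood at 114 per group, the share of studies with no finite any-pathogen odds ratio is about 99.5% at the printed rates, 32% at 1% and 46%, and 10% at 2.0% and 7.3%. The share is larger for rarer single pathogens. The figures assume independent women, the full 114 analysed in each group and an unadjusted model; losses would make them worse.

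The gap in section 12 is real under every reading examined, but how serious it is depends on rates that the document leaves in conflict. The case rests on the regression. Replacing chi-square by an exact test in sparse tables is a sensible precaution with a trade-off, and the verdict does not depend on it.

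**What to change.** In section 12, item c:
- For every pathogen odds ratio, any-pathogen and single-pathogen, adjusted or not, pre-specify Firth-penalised logistic regression with profile-likelihood confidence intervals, or exact logistic regression. Name the outcome and the covariates.
- For pathogen tables with an expected cell below 5, use Fisher's or an unconditional exact test with an exact confidence interval. Chi-square can stay elsewhere.
- State what will be reported for a pathogen found in no woman: the counts and an exact upper limit for each rate, with no odds ratio.

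In sections 1.2 and 6.1.2, reconcile the infection rates, say whether the percent signs are intended, and give the interval width and confidence level behind 114. If the printed rates are confirmed, the sample size must be reconsidered, because a change of method will not rescue it.

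The section 12 change is wording only and needs no new data or visits. The price is slight shrinkage of the odds ratio with Firth's method and some conservatism in the exact tests.
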